#### 8.4.2 Core Reading Center

The reading process with 6 radiologists selected for the feature comparison reader study will be conducted at International HealthCare, LLC in Norwalk, CT.

#### 8.4.3 Preparation of Cases for Interpretation

To maintain subject confidentiality, no identifying patient data will be displayed. Unique image identifiers associated with the case ID number will be visible in each DICOM header for tracking purposes. To maintain reader confidentiality, a unique ID number will be assigned to each radiologist participating in the reader study for entry on the CRFs.

### 8.4.4 Workflow for the Interpretation of Cases

Readers will be shown side-by-side images of the same breast reconstructed with the modified and original processing methods. One breast per subject (two views per breast) will be assessed by the readers. Readers will be blinded to the image reconstruction and processing methods. Each reader will be given a unique sample of cases to review. The order of the subjects and location (left or right review workstation high resolution monitor) of the images with modified processing will be randomized for each reader.

Within each stratum, cases will be randomly selected so that 10% have extremely dense breasts, 40% have heterogeneously dense breasts, 40% have scattered fibroglandular breasts, and 10% have fatty breasts.

Readers may interpret the preloaded cases in their assigned randomized order with the use of barcode scanner/barcodes.

#### **General instructions** for the readers are as follows:

The reader is to compare the tomosynthesis image on the left monitor to the tomosynthesis image on the right monitor. One CRF will be completed for each view (CC and MLO) for each case (breast).

For each case that has a lesion, the reader is to document lesion type, quadrant and slice number.

A study scribe representing the sponsor will capture the radiologist's results on the CRFs to ensure completeness and allow the radiologist to focus on evaluation of image sets.

### 9. Statistical Analysis

The proportion of cases where the readers judged the modified image processing as non-inferior will be calculated. Non-inferiority will be defined as a score of equivalence between modified and original or a score indicating the modified image processing is superior. For each reader, the proportion of cases judged as non-inferior with modified processing will be calculated for each feature and each view in Table 3. A pooled estimate will also be calculated where the results over all readers and views will be combined. 95% percentile bootstrap CIs will be constructed for the pooled proportions of cases judged as non-inferior with the modified processing. These CIs will be reported for each feature.

The null hypothesis is that the pooled proportion of cases judged as non-inferior with modified image processing is  $\leq$ 0.50, versus the alternative hypothesis that the pooled proportion is >0.50. If the 95% CI does not contain values  $\leq$ 0.50, then the null hypothesis will be rejected. These hypotheses will be evaluated for each of the seven general mammographic features. If the null hypothesis is rejected for each of the seven general features, then it will be concluded that the readers' subjective evaluation of the features on the modified imaging is non-inferior to the original imaging.

#### 9.1. Analysis Set

We plan to include all readers' interpretations of all cases in the analysis set. If any protocol deviations or violations occur, Fujifilm will report these to the statistician. The statistician will evaluate these to determine their impact on the validity of the study data and will determine whether any affected data points should be excluded from analysis.

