#### 10.5 Data Collection and Management

#### 10.5.1 General

All data entry will be completed using paper Case Report Forms, following the guidelines established in the Data Management Plan.

The privacy of participating subjects must be maintained in accordance with the HIPAA privacy ruling and disclosed per 24CFR50.

The CRFs will be data entered, and then reviewed for accuracy and completeness by a study monitor representing Fujifilm, as well as reviewed by DMC staff prior to data transfer to the statistician.

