### 10.5.2 Data Management Center

The responsibilities of the DMC will include monitoring and oversight of the collection efforts, performance of the data audits, facilitating data entry into a computerized database, and providing the data to the statistician.

The DMC responsibilities will include oversight of the data collection efforts (excluding image data, which will be collected by Fujifilm or its designees), facilitation of data entry into the computerized database, all final data cleaning, and performance of a final data quality-control audit prior to database lock.

CRFs will be logged and tracked when received by the DMC. CRFs will then be entered and stored in a 21 CFR Part 11 compliant clinical database. Upon completion of the study and resolution of all outstanding DCFs, the database will be locked and datasets necessary for analysis and reporting will be generated and provided to the statistician for final analysis.

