Statistical Analysis Plan

July 16, 2018

FMSU2017-003: A Feature Comparison Study to Evaluate the Modified Processing of Fujifilm's ASPIRE Cristalle with Digital Breast Tomosynthesis Option as Compared to the Original Processing

FUJIFILM Medical Systems U.S.A., Inc.

NCT03586583

Statistical Considerations for FUJIFILM Medical Systems, U.S.A., Inc. protocol FMSU2017-003

1. Statistical Analysis Plan:

The primary objective of the study is to test the non-inferiority of the modified processing in each of 7 general mammographic features. The proportion of cases where the readers judged the modified image processing as non-inferior will be calculated. Non-inferiority is defined as a score of equivalence between modified and original processing or a score indicating the modified image processing is superior. For each reader, the proportion of cases judged as non-inferior with modified processing will be calculated for each feature and each view. A pooled estimate will also be calculated where the results over all readers and views will be combined. 95% percentile bootstrap CIs will be constructed for the pooled proportions of cases judged as non-inferior with the modified processing. These CIs will be reported for each feature.

The null hypothesis is that the pooled proportion of cases judged as non-inferior with modified image processing is ≤ 0.50 , versus the alternative hypothesis that the pooled proportion is >0.50. If the 95% CI did not contain values ≤ 0.50 , then the null hypothesis will be rejected. These hypotheses will be evaluated for each of the seven general mammographic features. If the null hypothesis is rejected for each of the seven general features, then it will be concluded that the readers' subjective evaluation of the features on the modified imaging is non-inferior to the original imaging.

2. Sample Size Justification:

The following assumptions were made for determining sample size for the primary objectives:

- One breast per subject (two views)
- Each of six readers scores an independent sample of cases; thus, there is no correlation between readers' interpretations.
- 50% of cases have dense breasts
- >80% power is required
- 2.5% type I error rate (Note that hypothesis rejection depends on the lower bound of the 95% CI being greater than 0.50.)

Based on these assumptions, sample size was determined as follows:

$$M = \frac{\{1.96 \times \sqrt{0.5(1-0.5)} + 0.84\sqrt{p(1-p)}\}^2}{[p-0.5]^2}$$

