- Block 3: same 50 breasts as in Block 1, but re-ordered and scored with the MLO view, and
- Block 4: same 50 breasts as in Block 2, but re-ordered and scored with the CC view.

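### Does Protocol 9.1 put the type I error at risk by letting the statistician exclude deviation-affected data points without stated criteria, unit, timing or blinding?

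*Protocol*

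**What the plan says.** Protocol 9.1 (Analysis Set) includes all interpretations of all cases. The sponsor reports any deviations to the statistician, who weighs their effect on the validity of the data and "will determine whether any affected data points should be excluded from analysis".

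Protocol 10.5.2 gives cleaning and the quality-control audit to the data management center. After lock, "datasets necessary for analysis and reporting will be generated and provided to the statistician for final analysis". An earlier paragraph of the same section also lists providing data to the statistician, without a time.

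Protocol 8.4.4 states the blinding: "Readers will be blinded to the image reconstruction and processing methods". In the reader instructions there, "A study scribe representing the sponsor will capture" the results, on one CRF per view. Under 10.5.1 the CRFs are reviewed "by a study monitor representing Fujifilm" and by data management staff.

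SAP section 3 separates the two views of a case. Block 3, for example, is the "same 50 breasts as in Block 1, but re-ordered and scored with the MLO view". SAP section 1 then says: "A pooled estimate will also be calculated where the results over all readers and views will be combined". The SAP has no section on analysis sets, deviations or exclusions.

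**The concern.** The scores are subjective, coded left versus right, and compared with a fixed bound of 0.50. The overall conclusion is drawn only "If the null hypothesis is rejected for each of the seven general features", so a single borderline feature can decide it. If exclusions were made with the scores and the left/right key in view, a few removals could carry that feature over the line, and a reader of the report could not tell.

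Three silences point that way. The only datasets whose transfer is timed reach the statistician after lock, and 9.1 does not place the decision before then. Blinding is stated for readers only, while people representing the sponsor record and check the scores. The term data points is undefined, so a deviation in one block might remove one view and leave a half-scored case. The SAP, dated two months after the protocol, settles none of this.

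**Working it through.** **1. The plan's own figures.** Protocol 9.3 uses M = {1.96·√0.25 + 0.84·√(p(1−p))}² / (p−0.5)², divided by six readers. At p = 0.55, 0.56, 0.57 and 0.60, M = 781.6, 542.1, 397.6 and 193.6, hence 131, 91, 67 and 33 per reader, as in Table 4. Power at p = 0.56 is Φ((0.06·√n − 0.98)/√0.2464). With n = 600 this is Φ(0.4897/0.4964) = 83.8%, which agrees with slightly more than 80%. It stays at 80% or above down to about 543 cases, so modest exclusions do not threaten power.

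**2. Exclusion unrelated to the scores.** Simulation of 600 cases × 2 views = 1,200 scores at a true proportion of 0.50, with a case-clustered 95% bound, 20,000 trials per setting, and within-case correlation ρ of 0, 0.5 and 1 (assumed; the documents give none):
- no exclusions: 2.5% to 2.6%
- 12 scores removed at random: 2.4% to 2.6%

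**3. Exclusion chosen to favour the modified processing.** In the same simulation, removing only unfavourable scores gives 4.5% to 5.7% for 12 scores and 7.8% to 10.9% for 24.

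**4. How many deviations that requires.** Only scores touched by a deviation can be excluded. At a true proportion of 0.50, about half of the affected scores are unfavourable if deviations are unrelated to the scores. Removing k unfavourable scores therefore needs about 2k affected ones, with every favourable one kept. By normal approximation, the feature passes when the favourable count exceeds (1200−k)/2 + 0.98·√((1+ρ)(1200−k)). That count has mean 600 and standard deviation 0.5·√(1200(1+ρ)).

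Worked case, k = 12 and ρ = 0: the threshold is 594 + 0.98·√1188 = 627.8, z = 27.8/17.32 = 1.604, error 5.4%.

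| Affected scores | Unfavourable removed (k) | Error, ρ = 1 | Error, ρ = 0 |
|---|---|---|---|
| 0 | 0 | 2.5% | 2.5% |
| 2 | 1 | 2.6% | 2.7% |
| 6 | 3 | 2.9% | 3.1% |
| 12 | 6 | 3.3% | 3.7% |
| 24 | 12 | 4.4% | 5.4% |

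The documents give no deviation rate. Reading takes place at one center on preloaded workstations, with trained scribes and CRF review.

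**5. The opposite rule.** Suppose every scored interpretation had to stay primary, and a deviation put the same processing on both monitors. A score of 0 counts as non-inferior. With 12 such scores retained among 1,200, all scored 0, the simulated error (40,000 trials) is 5.4%, 4.7% and 4.4% at ρ = 0, 0.5 and 1. Readers are told to use 0 sparingly, so this too is a ceiling. It is about as large as the harm from 12 selective exclusions.

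**6. The half-scored case.** Scores are recorded per view, and proportions are computed per feature and view and then combined over views. Read naturally, a case with one remaining view contributes one score.

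**The case for a change.** The strongest case for a change is that it would be cheap. A short SAP section could name the deviation types and the unit, require the decision before lock and without the key, and ask for results with and without the excluded points. No case or reading would be added, and the data support a PMA supplement. The error figures in step 3 stand as arithmetic, and the all-seven rule gives little protection when six features pass clearly and one is borderline.

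The textual gap also stands: neither document gives criteria, unit, timing or blinding for exclusions. Several of its supports are weaker than they look. The documents leave open whether the decision comes before or after data transfer. If the statistician does receive scores only after lock, a decision made when a deviation is reported would be made without them, which is protective. Nothing says that the scribe or the monitor holds the left/right key, and 9.1 gives neither any say over exclusions. Loss of a whole reader (6.9% to 7.0% if the least favourable of six is dropped) goes beyond a clause about affected data points.

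**Conclusion.** No change to the plan is called for. This is missing detail that a competent analyst fills sensibly, by deciding and documenting any exclusion before linking scores to the key and by showing the result with and without it. Following 9.1 as written means full inclusion, with removal only of points whose validity a deviation has damaged. If that removal is unrelated to the scores, the error per feature stays near 2.5%. The figures of 4.5% to 5.7% (12 scores) and 7.8% to 10.9% (24 scores) are ceilings. They assume deliberate selection towards the modified processing and about twice as many affected scores as are removed. Making the all-scores result primary in every event would be no clear gain, since invalid scores of 0 could raise the error to 4.4% to 5.4%. No stated figure is wrong. The conclusion rests on an assumed within-case correlation of 0 to 1 and on deviations arising independently of the scores.

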### 9.2 Analysis of Primary Objective

The primary objective of this study is non-inferiority in each of the seven general mammographic features of the modified processing.

The proportion of cases where the readers judged the modified image processing as non-inferior will be calculated. Non-inferiority will be defined as a score of equivalence between modified and original or a score indicating the modified image processing is superior. For each reader, the proportion of cases judged as non-inferior with modified processing will be calculated for each general mammographic feature. A pooled estimate will also be calculated where the results over all readers will be combined. 95% percentile bootstrap CIs will be constructed for the pooled proportions of cases judged as non-inferior with the modified processing. These CIs will be reported for each of the 7 general mammographic features.

#### 9.3 Sample Size Justification

The following assumptions were made for determining sample size for the primary objectives:

- One breast per subject (two views)
- Each of six readers scores an independent sample of cases; thus, there is no correlation between readers' interpretations.
- 50% of cases have dense breasts
- >80% power is required

• 2.5% type I error rate (Note that hypothesis rejection depends on the lower bound of the 95% CI being greater than 0.50.)

Based on these assumptions, sample size was determined as follows:

$$M = \frac{\{1.96 \times \sqrt{0.5(1 - 0.5)} + 0.84\sqrt{p(1 - p)}\}^2}{[p - 0.5]^2}$$

where p is the proportion of comparisons judged as non-inferior under the alternative hypothesis. The sample size is given by N=M/(# readers). Table 4 summarizes the number of subjects needed per reader as a function of the proportion of cases judged as non-inferior with the modified processing.

Table 4. Number of Subjects Needed Per Reader for Tests of Non-inferiority

# readers	Proportion of Comparisons Judged as Non-inferior with Modified Processing (DVIIm plus ISR)				
	0.55	0.56	0.57	0.60	
6	131	91	67	33	

A study with 600 total subjects (i.e. 100 cases evaluated per reader) is proposed. This sample size would provide slightly more than 80% power to reject the primary null hypothesis, as long as  $\geq$ 56% of cases are judged non-inferior.

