# 3. Protocol Synopsis

SPONSOR NAME	FUJIFILM Medical Systems U.S.A., Inc.
PROTOCOL NUMBER	FMSU2017-003
STUDY TITLE	A Feature Comparison Study to Evaluate the Modified Processing of Fujifilm's ASPIRE Cristalle with Digital Breast Tomosynthesis Option as Compared to the Original Processing
DEVICE NAME	Fujifilm ASPIRE Cristalle with DBT Option Utilizing ISR and DVIIm
PURPOSE	The purpose of the feature comparison study is to evaluate general mammographic features in images of the same breast when reconstructed with modified (ISR and DVIIm) processing as compared to the original processing (FBP with EDR and MFP).
	One breast per subject (two views per breast) will be assessed by approximately six (6) readers.
STUDY OBJECTIVES	The following primary objectives will be tested simultaneously, and include:
	Non-inferiority in each of 7 general mammographic features of the modified processing
CORE READING CENTER	The feature comparison study will be performed at International HealthCare, LLC in Norwalk, CT.
PRINCIPAL INVESTIGATOR	The principal investigator for this study is [name], MBA, FACR, FSBI.
AND READERS	The feature comparison study radiologist readers shall meet all criteria for their respective roles as specified in the investigational plan.
	The feature comparison study readers will participate in a training session to ensure their understanding of the ASPIRE Bellus II workstation, the protocol, the study CRFs, study processes, GCP, and their obligations as study participants.

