#### STUDY ANALYSIS

The proportion of cases where the readers judged the modified image processing as non-inferior will be calculated. Non-inferiority will be defined as a score of equivalence between modified and original or a score indicating the modified image processing is superior. For each reader, the proportion of cases judged as non-inferior with modified processing will be calculated for each feature and each view. A pooled estimate will also be calculated where the results over all readers and views will be combined. 95% percentile bootstrap CIs will be constructed for the pooled proportions of cases judged as non-inferior with the modified processing. These CIs will be reported for each feature.

The primary objective is the readers' assessment for each of the 7 general mammographic features. The null hypothesis is that the pooled proportion of cases judged as non-inferior with modified image processing is <0.50, versus the alternative hypothesis that the pooled proportion is >0.50. If the 95% CI does not contain values <0.50, then the null hypothesis will be rejected. These hypotheses will be evaluated for each of the 7 general mammographic features. If all 7 null hypotheses are rejected, then it will be concluded that the modified imaging features are non-inferior to the original imaging

May 15, 2018 Confidential Page 13 of 31 DOC-0038502-A

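### The stated 80% power is for one feature; the planned conclusion needs all seven, and no power is given for that

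*Protocol*

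**What the plan says.** Protocol 9.3 introduces its inputs with "The following assumptions were made for determining sample size for the primary objectives" (plural) and requires at least 80% power. The formula that follows tests a single proportion against 0.50, and the total is divided among the readers: "The sample size is given by N=M/(# readers"). The resulting claim is in the singular: "This sample size would provide slightly more than 80% power to reject the primary null hypothesis", on condition that at least 56% of cases are judged non-inferior. SAP section 2 repeats both the formula and the claim.

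The decision rule covers seven features. The synopsis (Study Objectives) says "The following primary objectives will be tested simultaneously, and include" non-inferiority in each of the seven. Its Study Analysis part says "If all 7 null hypotheses are rejected, then it will be concluded that the modified imaging features are non-inferior to the original imaging". Protocol section 9 and SAP section 1 use the same rule: "If the null hypothesis is rejected for each of the seven general features, then it will be concluded" that the modified processing is non-inferior.

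On the two views, protocol section 9 says "A pooled estimate will also be calculated where the results over all readers and views will be combined", and SAP section 1 agrees. Protocol 9.2 mentions pooling over readers only. SAP section 3 has each reader score both views of the same breasts; Block 3, for example, is the "same 50 breasts as in Block 1, but re-ordered and scored with the MLO view".

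The listed assumptions include neither the number of features, nor a correlation between features, nor a correlation between views.

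**The concern.** When a conclusion requires seven separate rejections, its power cannot exceed that of the weakest test, and it is normally lower. A reader of 9.3 will take the 80% at 56% as the study's chance of success, because the section says it sizes the study for the primary objectives and the plan draws only one conclusion. The figure given is the chance for one feature taken alone.

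What is at stake is an undisclosed risk of missing the overall conclusion because a single feature falls short. Error control is not in question: since every null must be rejected, testing each at one-sided 2.5% needs no multiplicity adjustment.

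**Working it through.** **Inputs from the documents.** One-sided type I error 2.5% (z = 1.96); required power 80% (z = 0.84); null proportion 0.50; alternatives 0.55, 0.56, 0.57 and 0.60; 6 readers with 100 cases each, n = 600; no correlation between readers; seven features, all to be rejected.

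**Inputs I had to assume.** A common correlation r between the seven test statistics (0, 0.5, 0.8, and up to 0.9 where stated); a between-view correlation c; no clustering of scores within a reader.

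**1. The plan's own table.** M = {1.96 × 0.5 + 0.84 × √(p(1−p))}² / (p − 0.5)², divided by 6 and rounded up.

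| p | M | M/6 | Rounded up | Table 4 |
|---|---|---|---|---|
| 0.55 | 781.6 | 130.3 | 131 | 131 |
| 0.56 | 542.1 | 90.3 | 91 | 91 |
| 0.57 | 397.6 | 66.3 | 67 | 67 |
| 0.60 | 193.6 | 32.3 | 33 | 33 |

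Table 4 is reproduced exactly.

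**2. Power for one feature.** Inverting the formula gives Φ[((p − 0.5)√n − 0.98)/√(p(1−p))]. With n = 600 and p = 0.56 this is Φ[(0.06 × 24.49 − 0.98)/0.4964] = Φ(0.987) = 83.8%. The exact binomial test (reject at 325 or more of 600) gives 82.8%. The plan's statement is therefore right, and it is a single-feature figure.

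**3. Power for all seven, n = 600.** With independent features this is the single-feature power to the seventh power: 0.838⁷ = 0.290. With equal correlation r it is the average over a standard normal x of {Φ[(z + √r·x)/√(1−r)]}⁷, where z = 0.987 at p = 0.56.

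| Proportion, all seven features | One feature | r = 0 | r = 0.5 | r = 0.8 |
|---|---|---|---|---|
| 0.56 | 83.8% | 29% | 52% | 66% |
| 0.57 | 93.1% | 61% | 74% | 83% |
| 0.58 | 97.6% | 85% | 89% | 93% |

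At 0.56 the ceiling is 83.8% (r = 1), and 80% is reached only at r of about 0.99.

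**4. Mixed proportions, n = 600.** One feature at 0.56 and six at 0.60: 83% to 84%. Two at 0.56 and five at 0.60: 70% (r = 0) to 79% (r = 0.9).

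**5. Counting the second view.** Two views per breast with correlation c give an effective n of 1,200/(1 + c). For c = 0.5 this is 800; for c = 0 it is 1,200. With all seven features at 0.56:

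| Effective n | r = 0 | r = 0.5 | r = 0.8 |
|---|---|---|---|
| 600 (no credit) | 29% | 52% | 66% |
| 800 (c = 0.5) | 58% | 72% | 82% |
| 1,200 (c = 0) | 91% | 93% | 96% |

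**6. What 80% for all seven would require.**

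| | r = 0 | r = 0.5 | r = 0.8 |
|---|---|---|---|
| Proportion on every feature, n = 600 | 57.8% | 57.3% | 56.8% |
| Proportion on every feature, effective n = 800 | 56.7% | 56.4% | 55.9% |
| Effective n if all are at 56% | 1,007 | 901 | 776 |
| Highest c that gives this n (1,200/n − 1) | 0.19 | 0.33 | 0.55 |

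**The case against.** The strongest defence is that no stated number is wrong. The claim refers to a single null, section 9 defines that null for one pooled proportion, and the sentence can be read as per feature. That is fair, and it is why this is a matter of labelling and omission rather than an error in Table 4. It does not supply the missing figure: 9.3 sets its 80% for the primary objectives, and the only conclusion drawn needs all seven.

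Second, the low figures describe an unfavourable corner. The 56% is a floor, all seven features need not sit on it, and independence is a bound, since one reader grades all seven features on the same image pair. Ties count as non-inferior, so with evenly split preferences and tie rate t the proportion is 0.5 + t/2: 12% ties give 56% and 16% give 58%. All this stands. The required proportion moves by less than two percentage points. But readers are told to score ties sparingly, and the documents give no expected value for any feature.

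Third, the second view adds information. It does, possibly enough. But both views show the same breast to the same reader, the plan's formula takes no credit for the second view, and 9.2 leaves views out of the pooling.

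Fourth, figures to a tenth of a percentage point are fragile. If readers are treated as random, a within-reader correlation of 0.01 (an assumption) gives a design effect of 1 + 99 × 0.01 = 1.99 and lowers even single-feature power at 56% to about 55%. This is a good reason to state the no-clustering assumption beside any all-seven figure.

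**Conclusion.** The concern holds. On the plan's own basis of one observation per breast, 80% power at 56% does not carry over to the planned conclusion unless the seven tests are almost perfectly correlated or nearly all features lie above 56%. The proportion needed on every feature is about 57% to 58%. With credit for a second view correlated 0.5 with the first, it is about 56% to 57%, so the requirement may in fact be met, but the plan does not show it.

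These ranges rest on assumed correlations between features (0 to 0.8) and views, equal proportions across features unless stated, and no within-reader clustering. A positive result would remain valid; only the risk of a missed conclusion is understated. This should be fixed, but it does not put the design in doubt.

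**What to change.** Keep the 600 cases. In protocol 9.3 and SAP section 2, label the existing figure as power per feature, and add either the all-seven power or the proportion needed for it, with the assumptions listed. Possible wording:

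> Counting one observation per breast and assuming no clustering within readers, 600 cases give about 84% power (normal approximation) for each single feature if 56% of comparisons are judged non-inferior. The study conclusion requires all seven features. With the same proportion on all seven, 80% power to reject every null needs about 57.8% (independent features), 57.3% (between-feature correlation 0.5) or 56.8% (0.8). If the two views correlate 0.5, the figures are about 56.7%, 56.4% and 55.9%.

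The sponsor should substitute its own correlations where it has data. If it relies on the second view, it should also make 9.2 agree with section 9 on pooling over views.

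The cost is a few sentences in each document, a less favourable headline figure, and a commitment to stated correlation assumptions.
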